Aim 4 (Exploratory) Conduct in-depth interviews with PWH of predominantly Mexican descent to explore their perceptions of HIV infection and preferences for health communication. Qualitative findings will be integrated with those from the NY and DR cohorts to detail variations and similarities, and identify areas for intervention refinement.

II. Background and Significance:

Latinos are the largest and fastest growing minority group in the United States (US)¹ and they are disproportionately affected by HIV.²⁻⁵ Latinos experience higher HIV prevalence, faster disease progression, more HIV-related deaths, and a marked delay in the diagnosis of new infections.^{2,4,6} Many factors contribute to HIV-related health disparities, of which low health literacy (LHL) is a major contributor.^{7,8} LHL is an established concern globally^{9,10} and Spanish-speaking, less educated, and/or foreign-born Latinos are more likely to have LHL than those born in the US.^{9,11} LHL can lead to lesser ability to self-manage which leads to worse health outcomes.^{10,12} The proposed intervention is designed to meet the self-management information needs of Latino PWH with LHL, which can lead to better health outcomes.¹³⁻¹⁵

Infographics are technologies that can help clinicians effectively provide health information to individuals with varying language capabilities and LHL.^{16,17} Communication regarding complex chronic conditions, such as HIV, is challenging, as providers must provide large amounts of data to patients in a meaningful way.¹⁸ This is especially difficult when a patient's preferred language and culture differs from that of their provider.^{2,19} When clinician-patient communication is enhanced, it can lead to better self-management by improving behaviors such as adherence to antiretroviral therapy (ART).²⁰⁻²² Infographics can improve clinical communication because, when rigorously designed, they contain a depth and breadth of content displayed in a visually logical way.^{23,24} This is useful amidst culture and language differences as infographics provide images familiar to patients, which can help explain complicated processes, augment attention span, and improve information recall.²⁵⁻²⁸ Infographics such as the ones in this intervention can, therefore, improve self-management by helping clinicians provide information in an understandable way.^{24,28}

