D. Description, Risks and Justification of Procedures and Data Collection Tools

Description of data collection tools

D.1. Individual interviews to adapt infographics to the Colorado context.

Participants will initially complete a brief demographic questionnaire. Then, they will complete individual interviews with a study team member. Interviews will be audio recorded and later professionally transcribed.

D.2. RCT

D.2.1. Medical record review

Data will be extracted from medical records after each study visit and will include the primary outcome CD4 count as well as most recent viral load and currently prescribed ART regimen.

D.2.2. Baseline assessments

Baseline assessment will be administered either virtually or in-person at baseline visits and will collect demographics (age, length of time living with HIV, sex, gender, income, level of education among others), assess health literacy levels with two validated assessments, the Short Assessment of Health Literacy - Spanish & English (SAHL S&E)⁶⁵ and the Newest Vital Sign (NVS),⁶⁶ include a measure of acculturation, the Short Acculturation Scale for Hispanics (SASH),⁶⁷ and all other outcome measures not extracted from medical records (Table 1).

D.2.3. Follow up assessments

Follow up assessments will be administered either virtually or in-person at 3-, 6-, and 9-month visits and will include outcome measures (Table 1) and open-ended questions exploring infographic usability, satisfaction with infographic design, and recommendations for improvement. Questions regarding interventionists' communication strategies and intervention delivery will be included to further assess intervention fidelity and enable assessment of providers' communication variability.

D.2.4. Semi-structured in-depth interviews

In depth interviews with patient participants at the CO site will be conducted using a rigorously developed iterative interview guide.⁶³ Interviews at the CO site will include questions and probes to generate an explanatory model of participants' experience living with HIV and communicating about it in a clinical setting,⁶⁸ this data was already collected from participants in the DR and NY in preliminary studies. Questions to obtain feedback on how to adapt infographics and clinical communication will be included for all participants. Interviews will be audio recorded and later transcribed.

D.2.5. Follow up interviews with interventionists

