To establish sample size for the RCT, we used a longitudinal power analysis approach for testing the “time averaged difference” in two group means for a continuous outcome over time.⁷² This effect size is analogous to Cohen’s D: $(\mu_1 - \mu_2)/\sigma$, where μ_1, μ_2 are the outcome means (averaged over time) in the treatment and control groups, and σ is the standard deviation of the outcome (assumed constant over time and equal for both groups).⁷³ Assuming a slightly less than “medium” effect size of D=0.45,⁷³ 80% power, and two-sided significance level $\alpha=0.05$, the required total sample size ranges from 68-126 depending on the assumed constant pairwise correlation between the 4 repeated measures (which we varied from 0.25 to 0.75) (Table 3). We conservatively assume a correlation of 0.75 which requires a total sample size of 126. To account for 22% attrition, higher than our attrition rate that we experienced in the pilot tests in the Dominican Republic (16%) to account for complications with this hard to reach population of Denver, we increased the sample size to 164 (161.5 rounded up to ensure equal numbers in each group).

Interviews with key stakeholders

Up to 15 interviews with key stakeholders will be conducted at each site (CO and DR). This is based on estimates that 12 interviews per site can lead to saturation of identified themes.^{74,75}

Summary of total sample size per site:

DR total # of participants to be consented to achieve study aims: 100 (maximum recruitment at this site will be 115 to account for failures and withdrawals).

Denver Health total # of participants to be consented to achieve study aims: 121 (maximum recruitment at this site will be 140 to account for failures and withdrawals).

Analytic plan for each study aim

Aim 1: See individual interviews in section C above.

Aim 2: *Conduct a multi-site randomized controlled trial to assess the efficacy of the intervention (infographics administered through a mobile app) as compared to standard care in improving treatment outcomes (CD4 count, viral load, self-efficacy to manage HIV, among others) of PWH and determine how resultant effects vary over time (baseline to 9-months) and between sites (US and CO).*

Table 3. Necessary sample size for testing the time-averaged difference between two groups of equal size				Primary	
		ρ (constant correlation of 4 repeated measures over time)			

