Effect Size (Average diff. in 2 group means over time, analogous to Cohen's D: $(\mu_1 - \mu_2)/\sigma$)		0.25	0.50	0.75	
0.20 (Small)		344	491	638	
0.35		113	161	209	
0.40		86	123	160	
0.45		68	97	126	
0.50 (Medium)		55	79	103	
0.80 (Large)		22	31	40	

Note: Calculations with 80% power and $\alpha=0.05$ with 4 repeated measures assuming exchangeable/ constant pairwise correlation " ρ " varied from 0.25 to 0.75.

Analysis: A linear mixed effect model (LMM) will be used to compare the effects of the two groups (treatment vs. standard of care) on the primary longitudinal outcome of CD4 count between baseline and the three follow up visit time points (3-, 6-, and 9-months). Subject-specific random intercepts and slopes will be used to model heterogeneity in the subjects' trajectories. Three primary tests will be considered: 1) testing the time-averaged difference in the outcome between the two treatment groups (main effect for treatment), and 2) test whether change-over-time differs between the two treatment groups (treatment*time interaction), and 3) test whether the treatment effect differs between the two sites (treatment*site interaction and treatment*site*time interaction).

Secondary Analyses: The same analysis plan will be repeated with the remaining longitudinal outcomes Table 2 of the Research Strategy section of this application. Linear mixed effect models (LMM) will be used for continuous outcomes (CD4 count, viral load, knowledge questions, engagement with health care provider scale, satisfaction with care,

self-efficacy, health related quality of life PROMIS-29), logistic generalized linear mixed effect model (GLMM) will be used for the dichotomous adherence score (SMAQ-6), and ordinal GLMM will be used for the health status assessment score while LMM will be used for the additional health status continuous score. Lastly, as a simpler alternative to longitudinal mixed effect models (that use all time points), standard general linear models will be used to model outcomes at 9 months adjusting for baseline, thus testing whether an outcome differs between the two interventions at 9 months.

The System Usability Scale (SUS) that providers complete during the second training session will be scored according to published guidelines.⁷⁶

D.9.4. Aim 3: Assess implementation factors of integrating the SMART on FHIR app into EHRs through in-depth interviews and leverage findings to ensure the app effectively interfaces with EHRs in the CO and the DR.

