HIV continues to be a global concern, but the focus on HIV treatment and research have shifted from considering HIV to be a devastating acute condition to a chronic condition that is manageable with optimal self-management and treatment adherence. This shift in attention and disease progression requires persons living with HIV to effectively manage their health for long periods of time. However, individuals with limited health literacy may have difficulty accessing and using the health information that enables this extended health management, especially when they are presented with information that is not culturally relevant or is language inappropriate. This study will contribute evidence to support the provision of health information to diverse Latino populations in numerous ways.

This study aims to develop and evaluate an evidence-based and culturally appropriate technology (infographics embedded in a mobile application) to facilitate HIV-related communication between Latino persons living with HIV and their clinicians. By incorporating these evidence-based infographics into an app that interfaces with EHRs both locally and globally, this work will contribute to the informatics literature regarding the effective development and implementation of SMART on FHIR apps at a global scale. Additionally, it will provide valuable information regarding the effectiveness of infographics at improving clinical communication between patients and providers, which has widespread relevance to the growing information visualization literature. Additionally, there is little in the literature regarding effective ways to tailor interventions to heterogeneous groups, as an intervention designed for one Latino group may not be relevant to others. This work will provide evidence-based guidance regarding methods to effectively tailor health related interventions to diverse Latino groups. Furthermore, this intervention is scalable and will be accessible to clinicians working with Latino patients with low health literacy in the United States and around the world.

Including an additional portion in this study to ascertain if the infographics are meaningful and acceptable to non-Latino persons with HIV will provide preliminary data about the generalizability of these infographics and set the stage for further scalability of the intervention so that more individuals in need are likely to benefit from it.

F. References

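### Baseline health literacy, the characteristic the intervention is designed around, enters no planned model, and no literacy-specific treatment effect is prespecified

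*Combined protocol and SAP*

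**What the plan says.** Section II (Background and Significance) lists low health literacy as a major contributor, among many factors, to disparities in HIV. It states the mechanism, "LHL can lead to lesser ability to self-manage which leads to worse health outcomes", and the purpose, "The proposed intervention is designed to meet the self-management information needs of Latino PWH with LHL".

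The RCT eligibility criteria in Section IV.B contain no literacy condition, and randomisation (Section IV.C) is stratified by site only. Section IV.D.2.2 says the baseline visit will "assess health literacy levels with two validated assessments", namely SAHL S&E and NVS. These are two instruments at one visit, not two time points.

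The Aim 2 analysis in Section IV.F specifies a linear mixed model for CD4 count with random intercepts and slopes. It has three primary tests: the time-averaged treatment difference, treatment by time, and treatment by site (with and without time). For the other outcomes, "The same analysis plan will be repeated with the remaining longitudinal outcomes". The only covariate adjustment named is for the baseline value, in the simpler 9-month model. Neither literacy instrument appears anywhere in the analysis plan.

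**The concern.** The plan gives literacy two roles, as a prognostic factor and as the characteristic that defines the intended patients, and then uses it for neither.

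- **Interpretation.** Effect modification is prespecified for site but not for the characteristic the intervention was built around. Anyone who later asks whether it works in low-literacy patients will get a post hoc answer. With two instruments, no stated cut-off and many outcomes, that answer is open to selective choice.
- **Precision.** In the time-averaged comparison most of the error is between patients, and that is the part a prognostic baseline covariate can reduce. The score is to be collected anyway.

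**Working it through.** **Inputs from the plan.** Section IV.F gives "effect size of D=0.45", "80% power, and two-sided significance level" of 0.05, an assumed correlation of 0.75 between repeated measures, and 126 evaluable patients. The note to Table 3 confirms the set-up: "Calculations with 80% power and $\alpha=0.05$ with 4 repeated measures".

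**Inputs assumed.** The documents give neither the correlation r of literacy with the patient-mean outcome nor the share of patients with low literacy. I use r = 0.1 to 0.3 and shares of 25% to 75%. Because the models contain site terms, r should be read as the correlation remaining after site.

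**Step 1: reproduce the plan's figure.**
- Variance of the 4-visit mean, in SD² units: v = (1 + 3 × 0.75)/4 = 0.8125, of which 0.75 is between patients.
- Total N = 4 × (1.960 + 0.842)² × 0.8125 / 0.45² = 125.97, so 126. This matches Table 3.
- Attrition: 126/0.78 = 161.5, raised to 164 for equal cells, as stated.
- Power at 63 per arm: SE = √(2 × 0.8125/63) = 0.1606, and Φ(0.45/0.1606 − 1.96) = 80.0%.

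**Step 2: add literacy to the time-averaged model.** The SE is multiplied by √(1 − r²).

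| r | SE reduction | Power at 126 |
|---|---|---|
| 0 | 0 | 80.0% |
| 0.1 | 0.5% | 80.4% |
| 0.2 | 2.0% | 81.6% |
| 0.3 | 4.6% | 83.6% |

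**Step 3: the 9-month model, which already adjusts for baseline.** Take the baseline correlation as 0.75 and literacy as correlated r with the outcome at both times.
- Residual variance without literacy: 1 − 0.75² = 0.4375.
- With literacy: 1 − (0.75² + r² − 2 × 0.75 × r²)/(1 − r²). At r = 0.3 this is 1 − 0.5175/0.91 = 0.4313.
- Further SE reduction: 0.07% (r = 0.1), 0.3% (r = 0.2), 0.7% (r = 0.3).

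**Step 4: the treatment-by-time test.** This is a within-patient contrast. A literacy main effect is constant over a patient's visits and cancels from it, so the gain is essentially nil.

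**Step 5: the effect at low literacy.** With a share q of 126 completers, split equally by arm:
- SE in the low-literacy group = √(4 × 0.8125/(126q)).
- SE of the interaction = √(4 × 0.8125/126 × [1/q + 1/(1 − q)]).
- Smallest interaction detectable with 80% power = 2.802 × that SE.

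| Low-literacy share | 95% CI half-width | Power for 0.45 SD in the group | Detectable interaction |
|---|---|---|---|
| 25% | 0.63 SD | 29% | 1.04 SD |
| 50% | 0.45 SD | 51% | 0.90 SD |
| 75% | 0.36 SD | 68% | 1.04 SD |

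At a 50/50 split, power for an interaction of 0.45 SD is 29%. Reaching 80% would need about 504 completers.

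**The case against.** The case for leaving the plan as it is has real force. Aim 2 concerns Latino PWH and asks about variation over time and between sites, and the plan tests both. Omitting an optional covariate from a randomised comparison causes no bias. Education, income and acculturation are also collected and not modelled, since baseline variables may simply describe the sample. The precision gain rests on correlations the documents do not supply, and for CD4 a useful one is least plausible. The SD-based figures do not carry over to the logistic model for the SMAQ-6. A literacy interaction would be weak, with a detectable difference at twice the design effect.

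All of that stands, and it limits the size of the point. It does not answer the gap itself. Of these baseline variables, literacy is the one Section II singles out as what the intervention is meant to address.

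Four stronger readings are tempting, and the documents do not support them:

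- *Literacy is the driver of outcomes.* Section II calls it a major contributor among many.
- *The trial yields no estimate for low-literacy patients.* The overall effect includes those who enrol, and the baseline scores would allow an unplanned subgroup estimate. Only a prespecified one is absent.
- *The closing summary of knowledge to be gained promises efficacy in this subgroup.* Its sentence, "this intervention is scalable and will be accessible to clinicians working with Latino patients with low health literacy", is about access and scale-up.
- *The stated power is compromised.* The sample size never relied on covariate adjustment.

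**Conclusion.** The point holds in a modest form. Literacy is central to the rationale and is measured with two instruments at baseline, yet it enters no planned model, and no literacy-specific effect is prespecified. This is a missed opportunity and a gap in prespecification. It is not an error in the primary test, which remains valid with its planned 80% power.

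The precision gain is small: 0.4 to 3.6 percentage points of power for r of 0.1 to 0.3, confined to the time-averaged comparison. It is more plausible for recall, engagement, satisfaction and self-efficacy than for CD4. The literacy-specific estimate would be imprecise. At a 50% share its half-width of about 0.45 SD equals the whole design effect, so it can inform but not decide. These sizes rest on the plan's variance structure and on assumed values of r and of the low-literacy share.

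**What to change.** Before data lock, amend Section IV.F to:

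1. Name one of the two instruments as the analysis measure.
2. Add its continuous baseline score as a covariate in the time-averaged models, mainly for recall, engagement, satisfaction and self-efficacy.
3. Prespecify one treatment-by-literacy term, labelled exploratory, for a short list of named outcomes. Where an outcome has two measures, as satisfaction does in Table 1, say which one.
4. Report the treatment effect with its 95% CI at low literacy, using the instrument's published cut-off, and write that cut-off into the SAP.

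If the sponsor prefers not to model literacy, the SAP should at least state that the scores are descriptive only.

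The cost is a paragraph of SAP text, one or two degrees of freedom per model, and one extra exploratory contrast per named outcome. No new data are needed beyond the baseline collection already planned. The documents do not say whether data lock has passed. If it has, the same analyses should be reported as post hoc.

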Permuted block randomization stratified by clinical site will be computer generated a priori and placed in ordered opaque envelopes by a study team member who is not recruiting; thus, group assignments will be blind to the study team.⁶¹ Procedures will then take place as described in Table 2.

Time intervals of study visits (baseline, 3-, 6-, and 9-months) were selected as CD4 count and viral load may change at three months after ART initiation.⁶² Study participants will have visits with interventionists (treatment group) or other providers (control group). Prior to the study, standard education at each site will be evaluated to ensure the only difference between treatment and control groups is the infographic intervention. The intervention will not be administered at 9-month visits to enable assessment of long-term effects. No extra time will be allowed for intervention study visits and participants will be reminded of visits via phone. Half of intervention visits (randomly selected) will be audio recorded and a checklist of intervention components will be independently completed by two study team members, then compared to verify intervention fidelity.

In-depth interviews with key stakeholders

Semi-structured individual interviews will be conducted with up to 15 clinicians at each site who provide patient education to establish preferences and recommendations for integrating the app into each EHR (Aim 3). Interview guides will be rigorously developed⁶³ and questions will be guided with a theoretical model.⁶⁴

Usability testing of Creole version of the mobile application

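### Site, the randomisation stratum, is not stated as a model term for the treatment main effect; if it is left out, that test is conservative and gives up some power

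*Combined protocol and SAP*

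**What the plan says.** Section IV.C (RCT study procedures) sets out "Permuted block randomization stratified by clinical site". The planned split is 82 patients per site, 41 per group. Section IV.B describes two different clinic populations: Denver is 85% male and 90% Mexican, while the Dominican site is 57% female and 81% Dominican.

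Section IV.F, Aim 2, Primary Analysis: "A linear mixed effect model (LMM) will be used to compare the effects of the two groups (treatment vs. standard of care") on CD4 count at baseline and 3, 6 and 9 months, with random intercepts and slopes for subjects. Three primary tests follow:

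1. the treatment main effect, read as a time-averaged difference;
2. treatment-by-time;
3. "test whether the treatment effect differs between the two sites (treatment*site interaction and treatment*site*time interaction").

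Site is named only in the third. The secondary outcomes repeat the same plan. The simpler 9-month general linear model is described as adjusting for baseline, with no mention of site.

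The sample size section assumes an "effect size of D=0.45", with "80% power, and two-sided significance level" 0.05, where sigma "is the standard deviation of the outcome (assumed constant over time and equal for both groups").

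**The concern.** Stratified randomisation forces the arms to be balanced on site. The treatment estimate is then free of between-site variation, whatever the model. A model without a site term does not know this: it leaves the site difference in the between-subject variance and reports a standard error that is too large. The test then rejects less often than its nominal 5%, and precision that the design has already secured goes unused.

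The two clinics differ in sex and national origin, so a difference in CD4 level is plausible, though the documents do not show one. The effect at stake is efficiency in the first primary test and in the linear secondary models built the same way. Bias and false positives are not at issue.

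**Working it through.** **Inputs from the documents (Section IV.F and Table 3):** D = 0.45; two-sided alpha 0.05; 80% power; m = 4 measures; exchangeable correlation 0.75; 22% attrition; equal arms and equal sites.

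**Reproducing the plan's figure.** The variance of a subject's four-visit mean, in units of the overall outcome variance, is (1 + 3 × 0.75)/4 = 0.8125. Total N = 4 × (1.960 + 0.842)² × 0.8125 / 0.45² = 125.97, so 126, as in "We conservatively assume a correlation of 0.75 which requires a total sample size of 126". With attrition, 126/0.78 = 161.5, which the plan raises to 164.

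**Assumption.** Two equal sites differ by s overall SDs in CD4 level. The documents give no value, so a range is shown. The between-site part of the variance of the subject mean is s²/4.

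**Test 1 at N = 126.**
- Model SE without site: √(4 × 0.8125/126) = 0.1606.
- True SE under stratification, which is also the SE with site in the model: √(4 × (0.8125 − s²/4)/126).
- Type I error without site: 2Φ(−1.96 × model SE/true SE).
- Power without site: Φ((0.45 − 1.96 × 0.1606)/true SE).
- Power with site: Φ(0.45/true SE − 1.96).

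| s | True SE | SE overstated by | Type I error without site | Power without site | Power with site |
|---|---|---|---|---|---|
| 0.2 | 0.1596 | 0.6% | 4.9% | 80.2% | 80.5% |
| 0.3 | 0.1584 | 1.4% | 4.7% | 80.3% | 81.1% |
| 0.5 | 0.1543 | 4.1% | 4.1% | 81.0% | 83.1% |
| 0.8 | 0.1439 | 11.6% | 2.9% | 82.6% | 87.8% |

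The forgone power runs from about 0.3 points (s = 0.2) to about 5 points (s = 0.8).

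**Test 2 (treatment-by-time).** Mixed models were fitted by REML to simulated data: 128 subjects, 40 replicates, with assumed intercept variance 0.70, slope SD 0.1 and residual SD 0.5. The mean SE of the interaction without and with a site main effect was 0.0434 and 0.0434 at s = 0.5, and 0.0438 and 0.0436 at s = 0.8. With a site difference in slope of 0.1 per visit (s = 0.5), adding site and site-by-time moved it from 0.0442 to 0.0435. This is a within-subject contrast, and the random intercept absorbs a difference in level.

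**9-month model adjusted for baseline, constant site shift.** The residual variance without site is 1 − 0.75² = 0.4375. With site it is w − c²/w, where w = 1 − s²/4 and c = 0.75 − s²/4. At s = 0.2, w = 0.99 and c = 0.74 give 0.4369; at s = 0.8, w = 0.84 and c = 0.59 give 0.4256. Leaving site out therefore overstates the SE by √(0.4375/0.4369), about 0.1%, up to √(0.4375/0.4256), about 1.4%.

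**The case against.** The strongest reply is that the plan nowhere excludes site. It speaks of a single mixed model and then lists three tests. By ordinary hierarchy, a model with treatment-by-site-by-time also contains site and site-by-time, so one common model may be intended. It is right that the text is silent rather than explicit, and a reader who concludes that tests 1 and 2 are specified without site goes further than the wording allows.

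The common-model reading does not settle the matter, though. Beside a treatment-by-site term, the treatment coefficient depends on coding. Under reference coding it is the effect at one site, with an SE about √2 = 1.414 times larger. Power is then about Φ(2.80/1.414 − 1.96) = Φ(0.02), or 51%, if sites are equal in size and effect. Under centred coding it is the average over sites. The plan does not say which. Nor does this reading help the 9-month analysis, which is a separate model.

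Three stronger readings are tempting and do not stand.

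- **Power falls below 80%.** This needs the planning SD to be a within-site SD with site variance added on top, which gives 79%, 78% and 74.5% at 0.3, 0.5 and 0.8 SD. The plan defines sigma as the SD of the outcome and mentions no within-site SD.
- **Treatment-by-time loses power too.** The simulated SEs show practically no change from a site difference in level, and only about 1.6% (0.0442/0.0435) in the one case tried with differing slopes.
- **Every secondary outcome is affected alike.** The formula is for a linear model of a four-visit mean; it does not cover the logistic and ordinal models planned for SMAQ-6 and the health status assessment.

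It also stands that differences in sex and origin do not establish a CD4 difference, and that common eligibility rules at the two sites may narrow one.

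**Conclusion.** The point holds in a limited form. The stratification factor is not stated as a term in the model behind the treatment main effect or treatment-by-time, nor in the 9-month model. If it is left out of the main-effect test, that test is conservative by an amount that depends on an unreported site difference: negligible at 0.2 to 0.3 SD, about 2 points of power at 0.5 SD, and about 5 points at 0.8 SD. These figures assume equal sites, the plan's exchangeable correlation of 0.75, 126 completers, and sigma read as the overall outcome SD. On that reading the stated 80% power is safe. The case for acting is that the change costs almost nothing and also settles what the treatment main effect means.

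**What to change.** In Section IV.F, Aim 2, state that site and site-by-time are fixed effects in the primary and secondary longitudinal models, and that site is a covariate in the 9-month model. State also that treatment-by-site and treatment-by-site-by-time are fitted only for test 3, so that the treatment main effect in test 1 is the effect across both sites.

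The cost is a sentence or two and a few degrees of freedom: one for site, plus one for site-by-time if time is linear or three if the four visits are categorical. No new data and no change to the sample size are needed.

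### Three CD4 tests are called primary with no decision rule; if either treatment-effect test may carry the claim at 0.05, two-sided familywise error reaches 9.75%, and the sized contrast appears to average in baseline

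*Combined protocol and SAP*

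**What the plan says.** In the Data Analysis Plan (section IV.F), the primary analysis for Aim 2 fits a linear mixed model to CD4 count at baseline, 3, 6 and 9 months, with random intercepts and slopes. It then lists the tests: "Three primary tests will be considered: 1) testing the time-averaged difference"; second, "test whether change-over-time differs between the two treatment groups (treatment*time interaction"; third, "test whether the treatment effect differs between the two sites (treatment*site interaction and treatment*site*time interaction". The tests are numbered, but no sequence, per-test significance level, success criterion or multiplicity control is given there or elsewhere.

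The sample-size section sizes one quantity, the standardised difference in "outcome means (averaged over time) in the treatment and control groups", with D=0.45, "80% power, and two-sided significance level" 0.05. Table 3 was computed "with 4 repeated measures assuming exchangeable/ constant pairwise correlation". The result is 126 participants at correlation 0.75, raised to 164 for 22% attrition.

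Under Secondary Analyses, CD4 appears again ("Linear mixed effect models (LMM) will be used for continuous outcomes (CD4 count, viral load"), and as a simpler alternative "standard general linear models will be used to model outcomes at 9 months adjusting for baseline".

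**The concern.** Tests 1 and 2 each bear on whether the intervention changes CD4. The plan does not say what the trial concludes if one is significant and the other is not. If whichever succeeds can be presented as the primary finding, the nominal 5% is not the error rate of the claim. The two tests can also differ widely in power for the same true effect, so the conclusion could depend on which one is reported.

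The second issue concerns power and does not affect type I error. A time average that includes a visit with no expected difference is a diluted measure of the effect, and the stated 80% power then rests on a larger post-baseline effect than D=0.45 suggests.

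**Working it through.** **Inputs from the documents.** D=0.45; two-sided alpha 0.05; 80% power; four measures; exchangeable correlation ρ of 0.25 to 0.75, with 0.75 chosen; N=126 (63 per arm); 22% attrition; visits at 0, 3, 6 and 9 months. The outcome SD is set to 1, since no CD4 SD is given.

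**Assumptions of this check.** Each test is run at two-sided 0.05 (the plan states that level only for sizing). Effect shapes and any random-slope variance are illustrative.

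**1. The plan's own figure.** N = 4(1.960+0.8416)² f / D², with f=(1+3ρ)/4. For D=0.45 this gives 67.8, 96.9 and 126.0 at ρ = 0.25, 0.50 and 0.75, which matches Table 3. Then 126/0.78 = 161.5, and the next number that divides equally over two sites and two arms is 164. The plan's figure reproduces.

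**2. Error rate for tests 1 and 2.** The slope weights sum to zero, so under exchangeable correlation the four-visit average and the linear time contrast are uncorrelated.
- Either test counts: 1 − 0.95² = 9.75%. For two-sided, jointly normal tests this is the maximum.
- With an assumed random-slope SD of 0.10 outcome-SD per month, the test statistics correlate at 0.34 to 0.36 and the error is about 9.4%.
- Errors in the intervention's favour only: 1 − 0.975² = 4.94% if independent, against 2.5% for one test.
- Test 1 alone: 5%.

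**3. Baseline in the average.** With zero expected difference at baseline, the four-visit average is 3/4 of the mean post-baseline difference.
- An average of 0.45 needs 0.45/0.75 = 0.60 SD after baseline.
- If the effect is 0.45 SD after baseline only, the average is 0.75 × 0.45 = 0.3375 SD. At ρ=0.75, power with N=126 is 55.6%, and 80% power would need 224 before attrition.

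**4. Power of the competing contrasts at N=126.** Power = Φ(δ/SE − 1.96), SE = √(2v/63). The variance v is (1+3ρ)/4 for the four-visit average, (1−ρ)/45 for the monthly slope, and (1+2ρ)/3 − ρ² for the baseline-adjusted average over 3, 6 and 9 months.

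| Assumed effect | Contrast | δ | ρ=0.25 | ρ=0.50 | ρ=0.75 |
|---|---|---|---|---|---|
| 0.45 SD at 3, 6, 9 months | Four-visit average | 0.3375 | 82% | 67% | 56% |
| | Treatment-by-time | 0.045/month | 50% | 67% | 92% |
| | Adjusted post-baseline | 0.45 | 97% | 97% | 99.8% |
| Linear to 0.45 SD at 9 months | Four-visit average | 0.225 | 48% | 36% | 29% |
| | Treatment-by-time | 0.05/month | 58% | 76% | 96% |
| | Adjusted post-baseline | 0.30 | 72% | 74% | 90% |

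With the same random-slope SD of 0.10 at ρ=0.75, the three contrasts in table order have 47%, 53% and 89% power for the sustained effect, and 24%, 61% and 56% for the linear one.

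**5. Sample size for the adjusted post-baseline average.** Same formula, with f=(1+2ρ)/3 − ρ².
- D=0.45: 67.8, 64.6 and 42.0 at ρ = 0.25, 0.50 and 0.75. The largest, 68/0.78 = 87.2, becomes 88 with equal arms.
- D=0.30 (the linear shape): 152.6, 145.3 and 94.5, so about 94 to 153. After attrition the upper end is 153/0.78 = 196, above 164.

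**The case against.** The best defence is that test 1 is evidently the efficacy test. Aim 2 has three parts (efficacy against standard care, variation over time, variation between sites), the three tests follow that order, and only the first is sized. On that reading tests 2 and 3 describe variation and the error is 5%. This is a fair reading and it makes 9.75% a conditional ceiling. It does not settle the matter: all three tests carry the primary label, and after randomisation a treatment-by-time difference is itself evidence of an effect.

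The sizing is also internally consistent, because D is defined on means averaged over time. The 56% power appears only when 0.45 SD is assigned to post-baseline visits, a shape the plan does not state. That baseline is one of the four measures is itself an inference, from the visit count and the model description, though both agree.

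Stronger readings that a reader might reach, and that the documents do not support:
- **Counting all three tests, or all four terms.** The site interactions test heterogeneity and are not routes to an efficacy claim.
- **Treating the 9-month model as another route to the primary claim.** It is listed as secondary. Only its order and error control are missing, and the second mention of CD4 may be a drafting slip in a list of outcomes by model type.
- **Using Table 2 to show that baseline CD4 precedes exposure.** Section D.2.2 limits the baseline assessment to measures not taken from records, and CD4 is taken from records. The zero expected baseline difference rests on randomisation.
- **Reading 9.75% as the chance of falsely declaring benefit.** It includes errors in either direction.

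**Conclusion.** The gap is real and should be fixed: more than one treatment-effect test on CD4 is labelled primary and nothing says which decides. The size of the problem depends on a choice the plan leaves open. It is 5% if only the time-averaged test counts and up to 9.75% two-sided if either test 1 or test 2 counts at 0.05. It would be wrong to say that the trial has a 9.75% error rate as written.

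The baseline point is a separate matter of power and of what is being estimated. The 80% power holds for a 0.45 SD four-visit average. Whether that is optimistic depends on how large the effect is after baseline and how it develops, which the plan does not specify.

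**What to change.** Make the following changes before CD4 is compared by arm, and date them, since the protocol version is September 2023 and the trial was planned to start in January 2021.

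1. Name one treatment contrast as the sole primary hypothesis at two-sided 0.05. Preferred: the baseline-adjusted average difference over 3, 6 and 9 months from the planned mixed model, written as an explicit contrast. Define baseline CD4 as a value drawn before first exposure, because records are reviewed after each visit.
2. Make treatment-by-time secondary and keep the 9-month baseline-adjusted CD4 model secondary. Test both for efficacy claims only after the primary contrast is significant, in a stated order.
3. Report the two site interactions as effect-modification estimates with confidence intervals.
4. Restate the sample-size basis for the chosen contrast. With a 0.45 SD post-baseline average and exchangeable correlation, 164 suffices. A smaller average effect or random slopes lowers power; the plan should say so, and this does not call for enrolling more.

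Keeping the four-visit average as primary also closes the multiplicity gap, provided the other tests are ordered behind it and the plan states that 80% power then needs 0.60 SD after baseline.

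The cost is analysis-plan wording and a revised sample-size paragraph. The downside is that a treatment-by-time or 9-month result cannot support an efficacy claim if the primary contrast fails. If the effect grows gradually, treatment-by-time can be somewhat more powerful than the preferred primary (96% against 90% at correlation 0.75, N=126).
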